8. DOSING DELAYS/DOSE MODIFICATIONS

Study participants will be monitored for AEs from the time of signing consent through 100-days after the date of the decision to permanently discontinue all study treatment (i.e., last dose). Participants will be instructed to notify their physician immediately for any occurring AE.

The following should be taken into consideration in decisions regarding dose modifications (reductions and/or delays) for treatment-related side effects.

Cabozantinib and Pembrolizumab have class-specific safety profiles based on their mechanism of action but may also cause AEs that overlap. For management of AEs that can be clearly attributed to Cabozantinib or Pembrolizumab, independent dose modification for either agent is allowed.

- Examples of VEGFR TKI associated AEs caused by Cabozantinib are hypertension and hand-foot syndrome.
- Examples of irAEs and common AEs caused by Pembrolizumab are fatigue,

musculoskeletal pain, decreased appetite, pruritus, diarrhea, nausea, rash, pyrexia, cough, dyspnea, constipation, pain, and abdominal pain.

- Examples of overlapping AEs are diarrhea and elevations in liver function tests.

Table 5. Dose Modifications.

Dose Level	Cabozantinib Dose	Pembrolizumab Dose
0 (starting dose)	40 mg, oral, qd	200mg, IV, Q3weeks
-1	20 mg, oral, qd	200mg, IV, Q3weeks
-2	20 mg, oral, qod	200mg, IV, Q3weeks
-3	Discontinue Cabo	200mg, IV, Q3weeks

Other allowed dose interruption for pembrolizumab

Pembrolizumab may be interrupted for situations other than treatment-related AEs such as medical / surgical events or logistical reasons not related to study therapy. Participants should be placed back on study therapy within 3 weeks of the scheduled interruption, unless otherwise discussed with the Sponsor. The reason for interruption should be documented in the patient's study record.

8.1 Concomitant Medications/Vaccinations (allowed & prohibited)

Medications or vaccinations specifically prohibited in the exclusion criteria are not allowed during the ongoing trial. If there is a clinical indication for one of these or other medications or vaccinations specifically prohibited during the trial, discontinuation from trial therapy or vaccination may be required. The final decision on any supportive therapy or vaccination rests with the investigator and/or the participant's primary physician. However, the decision to continue the participant on study intervention requires the mutual agreement of the investigator, the Sponsors (Exelixis & Merck), and the participant.

Acceptable Concomitant Medications

All treatments that the investigator considers necessary for a participant's welfare may be administered at the discretion of the investigator in keeping with the community standards of medical care. All concomitant medication will be recorded on the case report form (CRF) including all prescription, over-the-counter (OTC), herbal supplements, and IV medications and fluids. If changes occur during the trial period, documentation of drug dosage, frequency, route, and date may also be included on the CRF.

Allowed anticoagulants are the following: prophylactic use of low-dose aspirin for cardio-protection (per local applicable guidelines) and low-dose low molecular weight heparins (LMWH); and therapeutic doses of LMWH or anticoagulation with direct factor Xa inhibitors rivaroxaban, edoxaban, or apixaban in subjects without known brain metastases who are on a stable dose of the anticoagulant for at least 1 week before first dose of study treatment without clinically significant hemorrhagic complications from the anticoagulation regimen or the tumor.

All concomitant medications received within 28 days prior to the first dose of trial intervention and up to 30 days after the last dose of trial intervention should be recorded. If participants experience an SAE or ECI, concomitant medications administered 30 days after the last dose of trial intervention are to be recorded.

8.2 Prohibited or Restricted Medications or Therapy

Participants are prohibited from receiving the following therapies during the Screening and Treatment Phase (including retreatment for post-complete response relapse) of this trial:

- Concomitant medications that are known to prolong the QTc interval should be avoided in subjects who receive Cabozantinib until they have permanently discontinued Cabozantinib treatment (refer to <http://www.qtdrugs.org> for a list of drugs which have the potential to prolong the QTc interval).
- Anticoagulation with coumarin agents (e.g., warfarin), direct thrombin inhibitors (e.g., dabigatran), direct factor Xa inhibitor betrixaban, or platelet inhibitors (e.g., clopidogrel) are prohibited.
- Co-administration of Cabozantinib with strong inhibitors of the CYP3A4 family may increase Cabozantinib concentrations and should be avoided. See **Appendix G**.
 - Strong CYP3A4 inhibitors: if possible, avoid concomitant use with Cabozantinib. Examples of strong CYP3A4 inhibitors include: Boceprevir, clarithromycin, conivaptan, indinavir/ritonavir, itraconazole, ketoconazole, lopinavir/ritonavir, atazanavir, telaprevir, telithromycin, nefazodone, nelfinavir, posaconazole, ritonavir, saquinavir/ritonavir, and voriconazole.
 - Grapefruit, grapefruit juice, star fruit and Seville oranges may also increase plasma concentrations of Cabozantinib and should also be avoided.
 - Other drugs that inhibit CYP3A4 should be used with caution because these drugs have the potential to increase exposure (AUC) to Cabozantinib.
 - Selection of alternate concomitant medications with no or minimal CYP3A4 enzyme inhibition potential is recommended.
 - When concomitant use of strong CYP3A4 inhibitors cannot be avoided, reduce Cabozantinib dose by 20 mg.
 - Resume Cabozantinib at the dose that was used prior to initiating the strong CYP3A4 inhibitor 2 to 3 days after discontinuation of the strong inhibitor.
- Chronic co-administration of Cabozantinib with strong inducers of the CYP3A4 may significantly decrease Cabo concentrations and should be avoided. See **Appendix F**.
 - Strong CYP3A4 inducers: if possible, avoid concomitant use with Cabozantinib. Examples of strong CYP3A4 inducers include: Rifampin, phenytoin, carbamazepine, rifabutin, rifapentine, phenobarbital and St. John's wort.
 - Other drugs that induce CYP3A4 should be used with caution as these drugs have the potential to decrease exposure (AUC) to Cabozantinib.
 - Selection of alternate concomitant medications with no or minimal CYP3A4 enzyme induction potential is recommended for subjects receiving Cabozantinib.
 - Caution must be used with discontinuing treatment with a strong CYP3A4 inducer in a subject who has been concurrently receiving a stable dose of Cabozantinib, as this could significantly increase exposure to Cabozantinib.
 - When concomitant use of strong CYP3A4 inducers cannot be avoided, increase Cabozantinib dose by 20 mg.
 - Resume Cabozantinib at the dose used prior to initiating the strong CYP3A4 inducer 2 to 3 days after discontinuation of the strong inducer.
 - Do not exceed daily dose of 60 mg (Cabozantinib).

- Antineoplastic systemic chemotherapy or biological therapy
- Immunotherapy not specified in this protocol
- Chemotherapy not specified in this protocol
- Investigational agents other than cabozantinib or pembrolizumab
- Radiation therapy: Radiation therapy to a symptomatic solitary lesion or to the brain may be allowed at the investigator's discretion.
- Live vaccines within 30 days prior to the first dose of study treatment and while participating in the study. Examples of live vaccines include, but are not limited to, the following: measles, mumps, rubella, varicella/zoster, yellow fever, rabies, BCG, and typhoid vaccine. Seasonal influenza vaccines for injection are generally killed virus vaccines and are allowed; however, intranasal influenza vaccines (e.g., FluMist®) are live attenuated vaccines and are not allowed.
- Systemic glucocorticoids for any purpose other than to modulate symptoms from an event of clinical interest of suspected immunologic etiology. The use of physiologic doses of corticosteroids may be approved after consultation with the Sponsors.

Participants who, in the assessment by the investigator, require the use of any of the aforementioned treatments for clinical management should be removed from the study. All treatments that the Investigator considers necessary for a participant's welfare may be administered at the discretion of the Investigator in keeping with the community standards of medical care.

Medications or vaccinations specifically prohibited in the exclusion criteria are not allowed during the ongoing study. If there is a clinical indication for any medication or vaccination specifically prohibited during the study, discontinuation from study therapy or vaccination may be required. The final decision on any supportive therapy or vaccination rests with the investigator and/or the participant's primary physician. However, the decision to continue the participant on study treatment requires the mutual agreement of the investigator, the Sponsor and the participant. However, the decision to continue the participant on study intervention requires the mutual agreement of the investigator, the Sponsors (Exelixis & Merck), and the participant.

There are no prohibited therapies during the Post-Treatment Follow-up Phase.

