3.2.13 Has a diagnosis of immunodeficiency (autoimmune disease) or is receiving chronic systemic steroid therapy (in dosing exceeding 10 mg daily of prednisone equivalent) or any other form of immunosuppressive therapy within 7 days prior to first dose of study treatment.

Note: Inhaled, intranasal, intraarticular, and topical corticosteroids and mineralocorticoids are allowed. Transient short-term use of systemic corticosteroids for allergic conditions (e.g., contrast allergy) is also allowed. Replacement therapy (e.g., thyroxine, insulin, or physiologic corticosteroid replacement therapy for adrenal or pituitary insufficiency, etc.) is not considered a form of systemic treatment and is allowed.

3.2.14 Has active autoimmune disease that has required systemic treatment in the past 2 years (i.e. with use of disease modifying agents, corticosteroids or immunosuppressive drugs). Replacement therapy (e.g., thyroxine, insulin, or physiologic corticosteroid replacement therapy for adrenal or pituitary insufficiency, etc.) is not considered a form of systemic treatment and is allowed.

3.2.15 Clinically significant cardiovascular disease, for example cerebrovascular accidents (less than 6 months, CVA) /stroke, myocardial infarction (also less than 6 months), unstable angina pectoris, New York Heart Association class 3 or 4 congestive heart failure, or serious cardiac arrhythmia requiring medication.

3.2.16 Uncontrolled hypertension defined as sustained blood pressure (BP) > 140 mm Hg systolic or > 90 mm Hg diastolic despite optimal antihypertensive treatment.

3.2.17 QT interval calculated by the Fridericia formula (QTcF) > 480 ms per electrocardiogram (ECG) within 14 days before first dose of study treatment.

Note: If a single ECG shows a QTcF with an absolute value > 500 ms, two additional ECGs at intervals of approximately 3 min must be performed within 30 min after the initial ECG, and the average of these three consecutive results for QTcF will be used to determine eligibility (i.e., if the average is ≤ 500 ms the patient is eligible).

3.2.18 Concomitant anticoagulation with or plan to use oral anticoagulants (warfarin, direct thrombin and Factor Xa inhibitors) or platelet inhibitors (e.g., clopidogrel). Allowed anticoagulants are the following:

- Prophylactic use of low-dose aspirin for cardio-protection (per local applicable guidelines) and low-dose low molecular weight heparins (LMWH).

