6.2 General Concomitant Medication and Supportive Care Guidelines

The chemotherapy pharmacist will review all medications (concurrent use of other all other drugs, over the counter medications or alternative therapies) for interactions at the start of therapy and new medications will be reviewed if started. The study team should check a frequently-updated medical reference for a list of drugs to avoid or minimize use of.

Rescue Medications & Supportive Care

Participants should receive appropriate supportive care measures as deemed necessary by the treating investigator. Suggested supportive care measures for the management of AEs with potential immunologic etiology are outlined along with the dose modification guidelines in the protocol. Where appropriate, these guidelines include the use of oral or IV treatment with corticosteroids, as well as additional anti-inflammatory agents if symptoms do not improve with administration of corticosteroids. Note that several courses of steroid tapering may be necessary as symptoms may worsen when the steroid dose is decreased. For each disorder, attempts should be made to rule out other causes such as metastatic disease or bacterial or viral infection, which might require additional supportive care. The treatment guidelines are intended to be applied when the Investigator determines the events to be related to pembrolizumab.

If after the evaluation of the event, it is determined not to be related to pembrolizumab, the Investigator does not need to follow the treatment guidance. It may be necessary to perform conditional procedures such as bronchoscopy, endoscopy, or skin photography as part of evaluation of the event.

Participant Discontinuation Criteria

Discontinuation of study intervention does not represent withdrawal from the study.

As certain data on clinical events beyond study intervention discontinuation may be important to the study, they must be collected through the participant's last scheduled follow-up, even if the participant has discontinued study intervention. Therefore, all participants who discontinue study intervention prior to completion of the protocol-specified treatment period will still continue to be monitored in this study and participate in the study visits and procedures, unless the participant has withdrawn from the study.

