If a participant withdraws from the study, they will no longer receive study intervention or be followed at scheduled protocol visits.

Specified details regarding procedures to be performed at the time of withdrawal from the study as well as specific details regarding withdrawal from future biomedical research are outlined in this protocol.

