Imaging: CT/MRI C/A/P	Within 8 weeks of treatment initiation	CT of the chest, abdomen, and pelvis or CT of the chest with MRI of the abdomen and pelvis will be performed in all subjects at screening and every 8 weeks (± 14 days) after first dose of Pembro/Cabo combination treatment for the first 6-months on-study or as clinically indicated. Upon completion of 6 months on study, these assessments will be performed every 12 weeks (± 7 days) up to 12-months post-treatment initiation. Tumor imaging will continue until either 12-months post-treatment initiation OR until radiographic disease progression per RECIST 1.1 as determined by the investigator. PR or CR per RECIST 1.1 at a given time point must be confirmed by repeat assessments ≥ 4 weeks after the criteria for response are first met.					

Correlative: Blood samples for Exosomal Lipids (optional)	
See ** below. These 7 blood draws for Exosomal Lipids are optional, and will be collected via another biospecimen sample collection protocol.
 
10cc blood in lavender-top tube w/ EDTA will be collected at the following 7 timepoints:
 
Pre-treatment baseline: i.e., predose Cycle 2 clinic visit Cycle 3 clinic visit Cycle 4 clinic visit Cycle 5 clinic visit Cycle 6 clinic visit Cycle 7 clinic visit
 
collected once monthly for 6-months (i.e., at clinic visit during Cycles 2 – 7). The first blood draw is prior to Cycle 1; the second blood draw occurs immediately prior to Cycle 2 (i.e., blood is drawn on day 1 of each cycle, up to Cycle 7).
						
Correlative: Archival Tumor (optional)	
*** If archival tissue is available, tumor tissue will be obtained via another protocol for biospecimen sample collection for correlative, patient-derived organoids. Patients enrolled on this trial will have to sign a separate consent for utilization of archival tissue.
						
Con Meds	X ¹	X ²	X ²	X ²	X ²	X ²	
Adverse Events	≤ 28 days	X	X	X	X	X	
Pembrolizumab (IV infusion)		X, q3 weeks for 8 cycles.		Could continue			
Cabozantinib (oral med)		C1 Day 1 dose given in clinic to monitor safety. C1 D2-D21 doses are taken at home.	X, Daily dose taken at home C2-C8	Could continue			
		Cabozantinib dispensed to subjects every 3 weeks.					
Cabozantinib daily dosing diary		The patient will record the daily amount of Cabozantinib taken in an oral medication log from Cycles 1-8 (i.e., C1D1 to C8D21).					

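### Section 8.2 removes from the study patients who need a listed therapy, in conflict with 6.2, 6.5 and the calendar; applied literally near progression, this could censor PFS events and bias the single-arm result upward

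*Combined protocol and SAP*

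**What the plan says.** Section 8.2 opens its list with "Participants are prohibited from receiving the following therapies during the Screening and Treatment Phase". The list covers, among others, drugs that prolong QTc, certain anticoagulants, strong CYP3A4 inhibitors and inducers, chemotherapy, other immunotherapy, radiotherapy, live vaccines and most systemic glucocorticoids. It ends by saying that participants who, in the investigator's assessment, "require the use of any of the aforementioned treatments for clinical management should be removed from the study".

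Other sections separate leaving treatment from leaving the study:

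- Section 6.2 says that "all participants who discontinue study intervention prior to completion of the protocol-specified treatment period will still continue to be monitored in this study", and names withdrawal of consent as the ground for withdrawal from the study. It gives the effect of withdrawal: "If a participant withdraws from the study, they will no longer receive study intervention or be followed at scheduled protocol visits".
- Section 6.5 follows patients for progression and survival up to 1 year from the start of therapy, or to death.
- The imaging row of section 11 says: "Tumor imaging will continue until either 12-months post-treatment initiation OR until radiographic disease progression per RECIST 1.1 as determined by the investigator".
- Section 6.4 and the early-discontinuation row of section 11 list stopping therapy and removal from the study as two different things.

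Section 8.2 is also not consistent with itself. Its radiotherapy entry says "Radiation therapy to a symptomatic solitary lesion or to the brain may be allowed", and unavoidable CYP3A4 drugs are handled within the entry ("When concomitant use of strong CYP3A4 inhibitors cannot be avoided") rather than by removal. A later paragraph speaks only of possibly stopping study therapy. On steroids, the note to 3.2.13 says "Transient short-term use of systemic corticosteroids for allergic conditions (e.g., contrast allergy) is also allowed"; the on-study steroid entry in 8.2 carries no such exception.

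Sections 9.4 and 9.7.2 put treated patients in the primary PFS analysis. Section 9.6 says that a patient without an event is censored. No section says how PFS is handled for a patient removed under 8.2, or for one who starts new anticancer therapy before documented progression.

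**The concern.** Some of the listed therapies, chiefly other anticancer treatment and steroids for symptoms, are likely to be needed when a patient is deteriorating. If such a patient leaves the study before a scan shows progression, the natural handling is censoring at a moment when an event is close. That censoring is informative.

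The one-sample log-rank test compares observed events with the number expected under the historical 2.0-month median. Removing a patient just before the event takes away one observed event and very little expected exposure. There is no control arm in which the same loss would cancel. With 21 evaluable patients, one or two such removals matter. Removal for any reason can also lose the 1-year survival status needed for the secondary endpoint in 1.2.4.

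**Working it through.** **Inputs from the plan (9.2, 9.6).** Median PFS 2.0 months (null) against 4.0 months (alternative), exponential; one-sided 5%, power 80%; 14 then 21 evaluable patients; limits 0.088 and 1.632; 1 patient per month; 6 months of follow-up after the last patient; 5% drop-out, 23 enrolled.

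**The plan's own figure.** With λ0 = ln 2/2 = 0.3466 and λ1 = ln 2/4 = 0.1733 per month, the one-sample log-rank sample size is n = (1.645·√v0 + 0.842·σ1)²/(v0 − v1)². Here v0 and v1 are the expected events per patient under the null and alternative hazards when the alternative is true, and σ1² is the exact variance. The per-patient follow-up used in the design is not stated. At 5 months, v0 = 1.159, v1 = 0.580 and σ1² = 1.105, so n = (1.771 + 0.885)²/0.580² ≈ 21. At 6 months n = 20 and at 4 months n = 24. Then 21/0.95 = 22.1, rounded up to 23. The stated 21 and 23 are reproduced, and the point does not affect them.

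**Baseline error rate.** Simulating the stated two-stage rule with Z = (E − O)/√E gives a false-positive rate of 3.6 to 3.9% for 3 to 12 months of follow-up per patient. With variance (O + E)/2 it is 4.8 to 5.7%. The runs below use the first form, baseline about 3.7%.

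**Why a few removals matter.** Under the null with monthly entry and follow-up of 6 to 26 months, E ≈ 21 − 0.43 = 20.6, so √E ≈ 4.54. A patient censored 0.5 month before the event lowers O by 1 and E by 0.3466 × 0.5 = 0.17. Z rises by about (1 − 0.17)/4.54 = 0.18. Two such patients add about 0.37, against a limit of 1.632. If removal is unrelated to progression, O and E fall together on average and Z is not shifted.

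**Exposure.** The first scheduled scan is at 8 weeks, or 56/30.4 = 1.84 months. With a 2.0-month median, 1 − 0.5^(1.84/2) = 47% of patients would have their event before then, so need for a listed therapy before any on-study scan is plausible.

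**Simulation under the null** (60,000 runs per scenario, exact event times, interim 1 month after patient 14). Removed shares are assumptions; the documents give none.

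| Share removed | All censored 0.25-1.0 month before own event | Half of removals unrelated to progression |
|---|---|---|
| 0% | 3.5-3.7% | 3.5-3.7% |
| 5% (about 1 of 21) | 5.3-5.9% | 4.2-4.6% |
| 10% (about 2) | 7.5-8.7% | 5.3-5.8% |
| 20% (about 4) | 13.7-18.5% | 7.6-9.1% |

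With 6 months of follow-up per patient and a 0.5-month lead, the typical Kaplan-Meier median is 2.1, 2.2 and 2.4 months at 5%, 10% and 20% removed, when the truth is 2.0. If all removals are unrelated to progression, the false-positive rate stays at 3.5 to 4.2% and the median at 2.0.

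**Retention alone.** Suppose the patient stays in follow-up but starts new anticancer therapy 0.5 month before the event would have occurred, and that therapy gives a further median of 1, 2 or 3 months (assumptions). The false-positive rate is then about 5%, 8% or 12% with 10% of patients affected, and about 7%, 15% or 25% with 20%. Counting the new therapy as an event gives about 3%.

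**The case against.** The strongest reply is that the rest of the protocol points to off treatment but still followed. Section 6.2 states the principle, 6.5 has no exception for removed patients, and the later wording in 8.2 speaks of stopping study therapy. A patient who deteriorates can stop treatment for clinical progression under 6.4 and then enters post-treatment follow-up, where 8.2 prohibits nothing. Scans are allowed when clinically indicated, and the notes to the response tables in 12.1.6 and 12.2.5 ask for objective progression to be documented even after treatment stops. Section 8.2 also lets the investigator give whatever treatment the participant's welfare requires.

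Much of this stands, and it limits the point in three ways. A reader might infer that PFS is biased upward as a matter of course. The documents do not support that: it needs literal application, actual loss of follow-up, and removal linked to coming progression. A reader might also infer that every patient who needs any listed therapy is removed; 8.2 has its own handling for CYP3A4 drugs, some radiotherapy and some steroids, and applies only during screening and treatment. And the contrast-allergy conflict, though real, is no evidence of bias, because contrast allergy has no evident link to progression.

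The reply does not dissolve the conflict. The trigger in 8.2 is needing the therapy during the treatment phase, so removal can come before follow-up starts. Because the protocol elsewhere distinguishes study removal from stopping therapy, the sentence is hard to read as meaning only the latter.

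**Conclusion.** The contradiction is established from the text. The bias is a conditional risk. For removals that all fall 0.25 to 1.0 month before the patient's own event, the false-positive rate goes from about 3.7% to about 5-6%, 7-9% and 14-18% at assumed shares of 5%, 10% and 20%. Those are upper figures for each share: with half of the removals unrelated to progression, the same shares give about 4-5%, 5-6% and 8-9%. The only loss rate in the documents is the 5% unevaluable or drop-out allowance, which was not set for this purpose.

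A reader might think that rewording 8.2 is enough. It is not, because keeping patients to RECIST progression after a new therapy can credit that therapy's effect to the regimen. The missing PFS rule for new anticancer therapy is the second half of the point. The matter should be fixed; nothing in the documents shows that the result will be biased.

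**What to change.** 1. Reconcile the removal sentence in 8.2 with 6.2, 6.5 and the calendar. Patients who need a listed therapy should stay in imaging follow-up until RECIST 1.1 progression or 12 months, and in survival follow-up to 1 year, unless consent is withdrawn. Whether study treatment continues is left to the sections that govern it.
2. In 9.4, state how PFS is handled when new anticancer therapy starts before documented progression and when a patient is removed without progression. Add a sensitivity analysis that counts removal or new anticancer therapy as an event.
3. Reconcile the on-study steroid entry in 8.2 with the note to 3.2.13, and the radiotherapy entry with the removal sentence. Which clinical rule applies is for the investigators to decide.

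The cost is a short protocol amendment and one additional analysis. The follow-up is already specified and the sample size stays at 21 evaluable and 23 enrolled. The downside is that a few PFS events will occur after non-protocol therapy, which the sensitivity analysis addresses. The change is best made early, because progression dates lost through removal may not be recoverable.
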